6.3.3. ATI Eligibility Criteria

At the Day 28 visit and prior to the Period 2 Day 35 visit, participants will be assessed to determine whether the criteria necessary to begin ATI are met. All of the following criteria must be met for a participant to begin ATI (Period 2):

- Viral load < 50 copies/mL
- CD4+ T cell count > 400 cells/ μ L
- Negative urine pregnancy test
- Participant has received VRC07-523LS, CAP256V2LS, and at least 3 of the 10 scheduled doses of VES.
- Participant confirms agreement to request their partners to use condoms throughout the ATI period.

The initiation of ATI (Period 2) may be postponed for up to 4 weeks after the last VES dose for participants to meet the above requirements. If a participant develops any other acute event during this time that may require treatment before the participant starts the ATI (Period 2), the investigator should consult with the medical monitor. The investigator may delay the initiation of the ATI (Period 2), after consultation with the medical monitor, for up to a further 4 weeks if it is determined that the participant may proceed to ATI (Period 2) once the acute event has been treated successfully. The investigator should consult with the medical monitor to determine if repeat assessments should be performed to re-confirm the participant's eligibility for the ATI (Period 2).

Participants who do not meet the requirements for ATI (Period 2) will complete an ESDD visit within 3 days of informing the investigator/site and may undergo early discontinuation of study follow up and procedures as described in Section [6.9.2](#).

6.4. Treatment Assessments—Period 2

Participants will have up to 18 visits over 15 weeks. Doses 4 to 10 of VES will be administered orally on Day 42, Day 56, Day 70, Day 84, Day 98, Day 112, and Day 126.

For Doses 4 to 10, 6 mg [3x2 mg tablets] or 8 mg [4x2 mg tablets]) will be administered per discussion with and approval from the Gilead medical monitor based on safety and tolerability of prior doses.

Participants will remain at the site for monitoring for at least 4 hours after VES dosing. If participants experience significant influenza-like AEs (eg, moderate or severe pyrexia, chills, headache, myalgia, fatigue, malaise, joint pain) after the first 2 VES doses, monitoring may be extended to > 4 hours for subsequent doses. Fasted status and food consumption will be checked prior to dosing.

No ART will be administered and ATI will start from Day 35.

If the ART restart criteria are met, the end-of-Period 3 visit (Section 6.5.2) will be completed and the participant may begin Period 4A.

Table 4. Period 2 Study Visits and Study Drug Administration

ATI = analytical treatment interruption; VES = vesatolimod
Every Period 2 study visit is based on the Day 0 visit + the number of postponement days required to confirm ATI eligibility in Period 1, if applicable

6.4.1. Treatment Assessments—Days 29 to 133

The following assessments are to be completed at every visit, unless otherwise specified. All study visits are to be completed within ± 3 days of the protocol-specified visit date (based on the Day 0 visit + the number of postponement days required to confirm ATI eligibility in Period 1, if applicable), and study procedures are to be completed within ± 2 hours of the protocol-specified time point. Symptom-directed physical examination

- Vital signs (blood pressure, pulse, respiration rate, oxygen saturation, and temperature) at:
 - Doses 4 to 10 of VES prior to administration and at 1, 2, and 4 hours after administration
(Day 42 and at each visit every 2 weeks thereafter)
 - If the participant experiences new or worsening symptoms, evaluate for signs and symptoms of CRS, including vital signs
- Body weight (Day 42 and at each visit every 2 weeks thereafter)
- Obtain blood samples for:
 - Plasma HIV-1 RNA **(Day 42 and at each visit every 2 weeks thereafter)**
 - If a confirmed rebound of ≥ 50 copies/mL occurs, the test should be completed weekly

- Plasma HIV-1 resistance testing (in case of viral rebound) to VRC07-523LS, CAP256V2LS, and baseline ART (**Day 42 and at each visit every 2 weeks thereafter**)
- Chemistry profile: ALP, AST, ALT, total bilirubin, direct and indirect bilirubin, total protein, albumin, CK, bicarbonate, BUN, calcium, chloride, creatinine, glucose, phosphorus, magnesium, potassium, sodium, uric acid (**Day 42 and at each visit every 2 weeks thereafter**)
- Hematology profile: CBC with differential and platelet count (**Day 42 and at each visit every 2 weeks thereafter**)
- Creatinine clearance according to the Cockcroft-Gault formula (**Day 42 and at each visit every 2 weeks thereafter**):
$$\text{Female Estimated Creatinine Clearance} = [(140 - \text{age in years}) \times (\text{weight in kg})]/[72 \times (\text{serum creatinine in mg/dL})] \times 0.85$$
- Anti-VRC07-523LS and anti-CAP256V2LS antibody profiling from serum (**Days 56, 84, 112, and 133**)
- HIV-specific antibody profiling using plasma (**Days 126 and 133**)
- Whole blood ISG mRNA panel (**Days 56, 57, 126, and 127**)
- Soluble proteins (cytokines, chemokines, and inflammatory markers) (**Days 56, 57, 63, 126, 127, and 133**)
- CD4+ and CD8+ T cell absolute count, percentage, and CD4/CD8 ratio (**Days 42, 56, 70, 84, 98, 112, 126, and 133**)
- PBMC sample for immune cell frequency, activation, and phenotyping (**Days 56, 57, 63, 126, 127, and 133**)
- PBMC sample for HIV-specific T cell responses (**Days 63 and 133**)
- Serum VRC07-523LS PK collection (**Days 56, 84, 112, and 133**)
- Serum CAP256V2LS PK collection (**Days 56, 84, 112, and 133**)
- Plasma dolutegravir PK collection (**Days 56, 84, 112, and 133**)
- Plasma sample for active HIV-1 reservoir (**Days 56, 57, 126, 127, and 128**)
- PBMC sample for active HIV-1 reservoir (**Days 56, 57, 126, 127, and 128**)

- Obtain urine collection for:
 - Urinalysis (**Day 42 and at each visit every 2 weeks thereafter**)
 - Urine pregnancy testing; a positive result will be confirmed with a serum pregnancy test. If the serum pregnancy test is positive, the participant will discontinue from study drug (**Day 42 and at each visit every 4 weeks thereafter**)
- Birth control will be checked and replaced, if required.
- Ongoing eligibility assessment prior to the participant being administered study drug on site (**Days 42, 56, 70, 84, 98, 112, and 126**)
 - Known HIV-1 seronegative sexual partners of enrolled study participants may be referred for HIV PrEP to decrease risk of HIV transmission during ATI.
- Adverse events and changes in concomitant medications will be assessed and recorded. Participants will be reminded to report all symptoms, including flu-like symptoms (eg, fatigue, pyrexia, chills, myalgia, joint pain, or headache) or other unexpected symptoms

6.5. Posttreatment Assessments—Period 3

Participants will have up to 14 study visits every 2 weeks for a total of 29 weeks.

No study drug (VES, VRC07-523LS, or CAP256V2LS) will be administered during this period.

No ART will be administered during this period and ATI will continue. If the ART restart criteria are met, the participant will stop Period 3, complete the end-of-Period 3 visit (Section 6.5.2), and may restart ART in Period 4A.

Upon completion of Period 3, all participants will be required to complete an end-of-Period 3 visit prior to moving into Period 4.

Table 5. Period 3 Study Visits and Study Drug Administration

	Period 3													
Week	21	23	25	27	29	31	33	35	37	39	41	43	45	47
Day	147	161	175	189	203	217	231	245	259	273	287	301	315	329
VES Dose	No dosing													
VRC07-523LS and CAP256V2LS Dose	No dosing													
ATI (Days 134 to 336)														

Every Period 3 study visit is based on the Day 0 visit + the number of postponement days required to confirm ATI eligibility in Period 1, if applicable

6.5.1. Treatment Assessments—Days 134 to 336

The following assessments are to be completed at every visit, unless otherwise specified. All study visits are to be completed within \pm 3 days of the protocol-specified visit date (based on the Day 0 visit + the number of postponement days required to confirm ATI eligibility in Period 1, if applicable), and study procedures are to be completed within \pm 2 hours of the protocol-specified time point.

- Symptom-directed physical examination (Day 147 and at each visit every 4 weeks thereafter)
- Vital signs (blood pressure, pulse, respiration rate, oxygen saturation, and temperature) (Day 147 and at each visit every 4 weeks thereafter)
- Body weight (Day 147 and at each visit every 4 weeks thereafter)
- Obtain blood samples for:
 - Plasma HIV-1 RNA
 - If a confirmed rebound of \geq 50 copies/mL occurs, the test should be completed weekly
 - Plasma HIV-1 resistance testing (in case of viral rebound) to VRC07-523LS, CAP256V2LS, and baseline ART
 - Chemistry profile: ALP, AST, ALT, total bilirubin, direct and indirect bilirubin, total protein, albumin, CK, bicarbonate, BUN, calcium, chloride, creatinine, glucose, phosphorus, magnesium, potassium, sodium, uric acid (**Day 147 and at each visit every 4 weeks thereafter**)
 - Hematology profile: CBC with differential and platelet count (**Day 147 and at each visit every 4 weeks thereafter**)
 - Creatinine clearance according to the Cockcroft-Gault formula (**Day 147 and at each visit every 4 weeks thereafter**):
Female Estimated Creatinine Clearance = $[(140 - \text{age in years}) \times (\text{weight in kg})] / [72 \times (\text{serum creatinine in mg/dL})] \times 0.85$
 - Anti-VRC07-523LS and anti-CAP256V2LS antibody profiling from serum (**Days 161, 189, 217, 245, 273, 301, and 329**)
 - CD4+ and CD8+ T cell absolute count, percentage, and CD4/CD8 ratio (**Day 147 and at each visit every 4 weeks thereafter**)

- PBMC sample for latent HIV-1 reservoir (**Day 147**)
- PBMC sample for testing of viral sensitivity to the VRC07-523LS and CAP256V2LS mAbs (**Day 147**)
- Serum VRC07-523LS PK collection (**Days 161, 189, 217, 245, 273, 301, and 329**)
- Serum CAP256V2LS PK collection (**Days 161, 189, 217, 245, 273, 301, and 329**)
- Plasma dolutegravir PK collection (**Days 161, 189, 217, 245, 273, 301, and 329**)
- From participants who provide additional consent, lymph node and/or GALT (GALT obtained by rectosigmoid biopsy) tissue collection (within window of \pm 5 days) will be taken at **Day 134** for some or all of the following tests:
 - Immune cell frequency, activation, and phenotype, gene expression and HIV-specific T cell response evaluation (PD and immunology)
 - HIV-1 reservoir measurements (virology)
- Obtain urine collection for:
 - Urinalysis (**Day 147 and at each visit every 4 weeks thereafter**)
 - Urine pregnancy testing; a positive result will be confirmed with a serum pregnancy test. (**Day 147 and at each visit every 4 weeks thereafter**)
- Birth control will be checked and replaced, if required.
- Known HIV-1 seronegative sexual partners of enrolled study participants may be referred for HIV PrEP to decrease risk of HIV transmission during ATI.
- Adverse events and changes in concomitant medications will be assessed and recorded. Participants will be reminded to report all symptoms, including flu-like symptoms (eg, fatigue, pyrexia, chills, myalgia, joint pain, or headache) or other unexpected symptoms.

At the end of Period 3, all participants will be required to complete an end-of-Period 3 visit prior to moving into Period 4.

6.5.2. End of Period 3 Visit

Participants who complete Period 3 or meet the ART restart criteria will be required to complete an end-of-Period 3 visit 1 week after their last visit (to be completed within \pm 1 day of the protocol-specified visit date [based on the Day 0 visit + the number of postponement days required to confirm ATI eligibility in Period 1, if applicable]). All participants will complete the following procedures:

- Symptom-directed physical examination
- Vital signs (blood pressure, pulse, respiration rate, oxygen saturation, and temperature)

- Body weight
- Review of AEs and changes in concomitant medications
- 12-lead ECG
- Obtain blood samples for:
 - Plasma HIV-1 RNA
 - Plasma HIV-1 resistance testing (in case of viral rebound) to VRC07-523LS, CAP256V2LS, and baseline ART
 - HIV-specific antibody profiling using plasma
 - Whole blood ISG mRNA panel
 - Soluble proteins (cytokines, chemokines, and inflammatory markers)
 - CD4+ and CD8+ T cell absolute count, percentage, and CD4/CD8 ratio
 - PBMC sample for testing of viral sensitivity to the VRC07-523LS and CAP256V2LS mAbs
 - PBMC sample for immune cell frequency, activation, and phenotyping
 - PBMC sample for HIV-specific T cell responses
 - PBMC sample for latent HIV-1 reservoir
 - PBMC sample for active HIV-1 reservoir
 - Plasma sample for active HIV-1 reservoir
- From participants who provide additional consent, lymph node and/or GALT (GALT obtained by rectosigmoid biopsy) tissue collection (within window of \pm 5 days) for some or all of the following tests:
 - Immune cell frequency, activation and phenotype, gene expression and HIV-specific T cell response evaluation (PD and immunology)
 - HIV-1 reservoir measurements (virology)

6.6. Posttreatment Assessments—Period 4

Participants who have remained virologically suppressed (plasma HIV-1 RNA < 50 copies/mL) or have not met the ART restart criteria at the end of Period 3 will continue into Period 4. The option will be available for either Period 4A, restart of ART for 12 weeks, or Period 4B, to remain off ART for a 12-week ATI extension. The period will begin after end of Period 3 Visit

to the end-of-study visit. The choice of Period 4A or 4B will be at the discretion of the participant and investigator.

Participants who meet the ART restart criteria prior to the end of Period 3 may also take part in Period 4A. The first Period 4A visit will require a urine pregnancy test. The ART restart criteria are:

- Plasma HIV-1 RNA measurements of \geq 1,000 copies/mL for 8 consecutive weeks AND no drop of $0.3 \log_{10}$ from the previous week
 - Once the first confirmed HIV-1 RNA value of \geq 50 copies/mL is detected, this will trigger weekly testing to monitor the HIV-1 RNA measurements,

OR

- Confirmed plasma HIV-1 RNA $>$ 100,000 copies/mL

OR

- If a confirmed CD4+ T cell count $<$ 350 cells/ μ L

OR

- If a participant becomes pregnant

OR

- ART may also be reinitiated during ATI per participant request, or at the discretion of the investigator, or sponsor due to other clinical criteria

Participants who restart ART in Period 4A will complete 6 study visits scheduled every 2 weeks over a 12-week period.

Participants who opt to remain off ART in Period 4B for the ATI extension will complete 6 study visits scheduled every 2 weeks over a 12-week period. If the participant's HIV-1 RNA remains at $<$ 50 copies/mL throughout Period 4B, additional procedures may be required at the end-of-study visit.

No study drug (VES, VRC07-523LS, or CAP256V2LS) will be administered in this period.

Table 6. Periods 4A and 4B Study Visits and Study Drug Administration

Periods 4A & 4B						
Week	49	51	53	55	57	59
Day	343	357	371	385	399	413
VES Dose	No dosing					
VRC07-523LS and CAP256V2LS Dose	No dosing					
4A: ART Restart 4B: ATI Extension Days 337 to 413						

VES = Vesatolimod, Every Period 4 study visit is based on the Day 0 visit + the number of postponement days required to confirm ATI eligibility in Period 1, if applicable

6.6.1. Treatment Assessments—Days 337 to 413

The following assessments are to be completed at every visit for Periods 4A and 4B, unless otherwise specified. All study visits are to be completed within \pm 3 days of the protocol-specified visit date (based on the Day 0 visit + the number of postponement days required to confirm ATI eligibility in Period 1, if applicable), and study procedures are to be completed within \pm 2 hours of the protocol-specified time point.

- Symptom-directed physical examination (**Day 343 and at each visit every 4 weeks thereafter**)
- Vital signs (blood pressure, pulse, respiration rate, oxygen saturation, and temperature) (**Day 343 and at each visit every 4 weeks thereafter**)
- Body weight (**Day 343 and at each visit every 4 weeks thereafter**)
- Obtain blood samples for:
 - Plasma HIV-1 RNA
 - Period 4A: If a confirmed rebound of \geq 50 copies/mL occurs, the test should be completed at each scheduled visit until the end-of-study visit
 - Period 4B: If a confirmed rebound of \geq 50 copies/mL occurs, the test should be completed weekly until ART restart criteria are met or the end-of-study visit
 - Plasma HIV-1 resistance testing (in case of viral rebound) to VRC07-523LS, CAP256V2LS, and baseline ART
 - Chemistry profile: ALP, AST, ALT, total bilirubin, direct and indirect bilirubin, total protein, albumin, CK, bicarbonate, BUN, calcium, chloride, creatinine, glucose, phosphorus, magnesium, potassium, sodium, uric acid (**Day 343 and at each visit every 4 weeks thereafter**)
 - Hematology profile: CBC with differential and platelet count (**Day 343 and at each visit every 4 weeks thereafter**)
 - Creatinine clearance according to the Cockcroft-Gault (**Day 343 and at each visit every 4 weeks thereafter**):
Female Estimated Creatinine Clearance = $[(140 - \text{age in years}) \times (\text{weight in kg})]/[72 \times (\text{serum creatinine in mg/dL})] \times 0.85$
 - CD4+ and CD8+ T cell absolute count, percentage, and CD4/CD8 ratio (**Day 343 and at each visit every 4 weeks thereafter**)

- Serum VRC07-523LS PK collection (**Days 343, 371, and 413**)
- Serum CAP256V2LS PK collection (**Days 343, 371, and 413**)
- Plasma dolutegravir PK collection (**Days 343, 371, and 413**) [**Period 4B only**]
- Anti-VRC07-523LS and anti-CAP256V2LS antibody profiling from serum (**Days 343, 371, and 413**)
- Obtain urine collection for:
 - Urinalysis (**Day 343 and at each visit every 4 weeks thereafter**)
 - Urine pregnancy testing; a positive result will be confirmed with a serum pregnancy test (**At the first ART visit/Day 343 and at each visit every 4 weeks thereafter**)
- Birth control will be checked and replaced, if required.
- Known HIV-1 seronegative sexual partners of enrolled study participants may be referred for HIV PrEP to decrease risk of HIV transmission during ATI (**Period 4B only**).
- Adverse events and changes in concomitant medications will be assessed and recorded. Participants will be reminded to report all symptoms, including flu-like symptoms (eg, fatigue, pyrexia, chills, myalgia, joint pain, or headache) or other unexpected symptom.

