To mitigate these risks, plasma viral load and CD4+ T cell count will be measured frequently during ATI, and ART will be promptly reinitiated according to the protocol-defined algorithm. Participants will also be monitored for AEs, and ART will be reinitiated if these are judged (by the investigator and/or sponsor) to be related to the ATI. The initial selection of participants who have a documented detection during acute HIV infection and timing of ART initiation, durable viral suppression for at least 12 consecutive months prior to the screening visit, and the availability of a fully active alternative ART regimen, in the event of discontinuation of the current ART regimen with development of resistance, will further minimize the risks of ATI.

Potential benefits include reduction of the latent HIV-1 viral reservoir, enhanced immune control of virus producing cells, and finally the combination of these effects on HIV-1 viral control (measured as plasma virus rebound and viral load set-point) in the absence of ART. There are no direct benefits to participants participating in this study.

During a pandemic, additional potential risks to the conduct of the study may include adequate study drug availability, interruptions to the study visit schedule, and adherence to protocol-specified treatment regimen, safety monitoring or laboratory assessments. Refer to [Appendix 7](#) for further details on the risks and risk mitigation strategy.

Considering the above, the benefit-risk balance for this study is considered positive.

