8.11. Sample Size

The sample size in this study is determined based on practical considerations and empirical experience with similar types of studies. No sample size and power calculation was performed. Up to 25 participants will provide a preliminary assessment of descriptive safety, efficacy, and PK.

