8.1.3. Statistical Analysis Methods

Individual participant concentration data and individual participant PK parameters for VES, VRC07-523LS, and CAP256V2LS will be listed and summarized using descriptive statistics for participants in the corresponding analyte PK analysis set. Summary statistics (number of participants, mean, SD, CV, median, min, max, Q1, and Q3) will be presented for both individual participant concentration data by time point and individual participant PK parameters. For individual participant concentration data for VRC07-523LS and CAP256V2LS, the summaries will only be presented through end of Period 3, since the actual time from study drug dosing varies depending on the time of ART restart for visits after end of Period 3 visit. Moreover, the geometric mean, geometric mean coefficient of variation (GCV), 95% CI for the geometric mean, and the mean and SD of the natural log-transformed values will be presented for individual participant PK parameter data.

Individual concentration data listings and summaries will include all participants with concentration data. If a participant has quantifiable pre-dose, BLQ at end of infusion, or received an incorrect dose, the related PK concentration(s) will be included in the table but will be excluded from the summary statistics, with reasons for exclusion identified. The sample size for each time point will be based on the number of participants with non-missing concentration data at that time point. The number and percentage of participants with concentration BLQ, as well as an indicator if more than one-third of the participants have concentration BLQ, will be presented for each time point. For summary statistics, BLQ values will be treated as zero at baseline and postdose time points. The method to handle BLQ values for PK summaries are described in Section 3.7. Concentration values will be presented as received from the bioanalytical lab and summary statistics will be presented to three significant digits.

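### The end-of-Period 3 and Period 4 visits carry two incompatible dating rules for participants who restart ART early, and the SAP corrects for the resulting mixed timing only in its antibody concentration summaries

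*Protocol*

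**What the plan says.** Early transition is planned. The Figure 2 footnotes in Section 3.2, together with Sections 6.4 and 6.5, let a participant who meets the restart criteria leave Period 2 or 3, complete the end-of-Period 3 visit and go to Period 4A. Section 7.3.2 provides for adverse event collection after such a move. Section 8.2.1.2 times the first internal analysis partly on participants who have already started Period 4A.

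The dating rules are these:

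- **Table 6 note (Section 6.6):** "Every Period 4 study visit is based on the Day 0 visit + the number of postponement days required to confirm ATI eligibility". The table gives one day range for both arms of Period 4: "4A: ART Restart 4B: ATI Extension Days 337 to 413".
- **Section 6.6.1:** the window is ±3 days, counted from a "protocol-specified visit date (based on the Day 0 visit + the number of postponement days required to confirm ATI eligibility in Period 1, if applicable". This covers Periods 4A and 4B alike.
- **Section 6.8:** the end-of-study visit uses the same Day 0 anchor with ±3 days.
- **Section 6.5.2:** the rule covers Period 3 completers and also those who "meet the ART restart criteria will be required to complete an end-of-Period 3 visit 1 week after their last visit". The same sentence requires that visit within ±1 day of a date counted from Day 0 plus postponement days.
- **Appendix 2a, footnotes f and g:** the end-of-Period 3 visit is tied to the last visit, and the end-of-study visit to the final Period 4 visit. Neither footnote mentions Day 0.

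On the analysis side, SAP 3.8.2 summarizes by nominal visit. SAP 8.1.3 leaves later visits, beyond Period 3, out of the antibody concentration summaries. Its stated reason is "since the actual time from study drug dosing varies depending on the time of ART restart for visits after end of Period 3 visit".

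**The concern.** For an early restarter the relative rule and the Day 0 rule name different dates, and the protocol does not say which one governs. A site that follows the relative rule breaches the written window, and a site that follows the window breaches the relative rule.

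The statistical consequence lies in the by-visit tables. If dates float, a sample recorded under a Period 4 label may come from a participant a few months after the Day 7 infusion or from one nearly a year after it. It may also come from someone on ART or someone still off it. SAP 3.2 and 3.4 define no split between Periods 4A and 4B. The SAP sees the problem for antibody concentrations and removes those visits. It has no matching rule for the by-visit summaries of HIV-1 RNA (6.3), laboratory values (7.2.1), vital signs (7.3) or antidrug antibodies (9.2).

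**Working it through.** This is calendar arithmetic. There is no power figure to reproduce (Section 8.11: "No sample size and power calculation was performed").

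**Inputs.** Last Period 3 visit Day 329 (Table 5). Period 4 visits Days 343, 357, 371, 385, 399 and 413 (Table 6). End-of-Period 3 visit = last visit + 7 (Section 6.5.2). Infusion on Day 7 (Section 6.3). No ATI postponement.

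**Reproducing the plan's grid.** 329 + 7 = 336 for the end-of-Period 3 visit; 336 + 7 = 343 for the first Period 4 visit; 343 + 5 × 14 = 413 for the last. The grid is consistent for a participant who completes Period 3.

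**Early restarter.** Let M be the day of the visit at which criteria are met.

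- Relative end-of-Period 3 date = M + 7.
- First Period 4A visit = M + 14. This assumes the same 7-day step as from Day 336 to Day 343.
- Gap between the two rules = 336 − (M + 7) = 329 − M. The gap for the first Period 4A visit is the same: 343 − (M + 14).
- Time since infusion at the first Period 4A visit, if dates float = M + 14 − 7 = M + 7.

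| Criteria met (M) | End-of-Period 3, relative | End-of-Period 3, Day 0 rule | Gap, days (weeks) | First 4A visit, relative | Days since infusion at that visit |
|---|---|---|---|---|---|
| 98 | 105 | 336 | 231 (33) | 112 | 105 |
| 133 | 140 | 336 | 196 (28) | 147 | 140 |
| 245 | 252 | 336 | 84 (12) | 259 | 252 |
| 301 | 308 | 336 | 28 (4) | 315 | 308 |
| 329 | 336 | 336 | 0 | 343 | 336 |

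Day 98 illustrates the eight-week viral load criterion counted from the Day 42 measurement (42 + 56 = 98). Every gap except the one at Day 329 exceeds both the ±1 and the ±3 day window. ATI postponement shifts both sets of dates equally and does not close the gap.

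**Effect on a by-visit cell.** If the first Period 4A visit is recorded under the Day 343 label, that cell could hold one sample taken 105 days after infusion and another taken 343 − 7 = 336 days after it. Antidrug antibodies are sampled at the Day 343, 371 and 413 visits. HIV-1 RNA is measured at every Period 4 visit. Laboratory tests and vital signs are done at the Day 343 visit and every 4 weeks after it.

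**The case against.** The best reply is that nobody would follow the Day 0 rule for an early restarter. Section 6.6 starts Period 4 after the end-of-Period 3 visit. Footnotes f and g of Appendix 2a are purely relative. Section 8.2.1.2 would make no sense if Period 4A could not begin before Day 337. SAP 8.1.3 takes floating dates for granted. This stands: floating dates appear to be what was meant. It does not change the written windows, which such visits cannot meet, and it is the reading under which the by-visit tables mix timings.

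The reply also limits what can be concluded. Three stronger readings are tempting:

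- **That ART is delayed for months, or that the schedule contradicts Section 1.5 ("ART will be promptly reinitiated according to the protocol-defined algorithm").** No passage says ART is first taken at the first Period 4A visit, and the Period 4 range opens on Day 337. Section 6.6 also allows reinitiation during ATI at participant request or at investigator or sponsor discretion. The phrase "At the first ART visit/Day 343 and at each visit every 4 weeks thereafter" in Section 6.6.1 can be read as listing alternatives, because the synopsis describes the pregnancy test schedule separately for Periods 4A and 4B.
- **That early restarters have no scheduled visits after restart.** Section 6.9.2 keeps a participant who stops study drug during ATI and reinitiates ART on the visit schedule.
- **That the main results are compromised.** Time-to-event endpoints use actual dates, and the set-point uses participant-specific dates (SAP 6.3). Treatment-emergent adverse events and laboratory abnormalities use the whole treatment-emergent period (SAP 7).

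It is also fair to say that the gap is small for anyone who meets criteria late in Period 3. The documents give no expected distribution of restart times.

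**Conclusion.** The protocol dates the end-of-Period 3 visit of early restarters by two rules that agree only for a last visit on Day 329, and it dates all their later visits from Day 0 without exception. The discrepancy is 329 − M days: 28 at Day 301, 84 at Day 245, 196 at Day 133 and 231 at Day 98. The apparent intent is floating dates. On that reading the written windows are wrong for these participants, and the descriptive by-visit summaries of HIV-1 RNA, laboratory values, vital signs and antidrug antibodies pool unlike times under one label.

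This rests on two assumptions. One is the 7-day step to the first Period 4A visit. The other is that re-dated visits are recorded under the Table 6 labels; the eCRF is not available to confirm this. The point is an internal inconsistency with a partial correction in the SAP. The documents do not support reading it as an instruction to withhold ART, and it does not affect the primary endpoints or the Kaplan-Meier analyses.

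**What to change.** 1. **Protocol.** The sponsor should reconcile Sections 6.5.2, 6.6.1, 6.8 and the Table 6 note with the early-transition passages (Figure 2 footnotes, Sections 6.4, 6.5, 7.3.2 and 8.2.1.2) and with footnotes f and g of Appendix 2a, so that one visit anchor applies to early restarters. Consistency with Section 1.5 should be checked at the same time. This review does not say which clinical timing is right.
2. **SAP or CSR.** Extend the 8.1.3 exception to the other by-visit summaries. One option is to present Period 4A data by actual weeks since ART restart, and antidrug antibody data by actual time since infusion, separately from Period 4B. The other is to limit by-visit summaries to visits before the end-of-Period 3 visit. In either case, handle the end-of-Period 3 visit of early restarters by its actual day. SAP Section 1 allows changes after finalization if the CSR documents them.

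The cost is wording in four places, a small extra derivation and fewer participants per by-visit cell. No visits or samples are added.
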